3.1.4. Long Term Extension Treatment Period (LTE) (up to 24 months)

Upon completion of the RW period and the EORW visit, all subjects that did not discontinue study drug will have an option to continue treatment with open-label rilonacept in the LTE or to withdraw from the study. Subjects still in the RI period at the time that the RW period has ended and the LTE is opened will have the option to enter the LTE directly when they have completed the RI period and have met the definition of clinical response or to withdraw from the study.

Treatment in the extension period may continue until the earliest of the following dates:

- Rilonacept is approved for commercial use or is available for reimbursement to treat pericarditis in the region
- The subject has received 24 months of treatment in the LTE or the Investigator and subject decide to continue in the study off-treatment
- Additional reasons for discontinuation of treatment can be found in section 4.3.1.

Any subject who, in the opinion of the Investigator, should not continue open-label rilonacept will be withdrawn from the study.

Subjects will be reviewed again at 18 months after their most recent recurrence, (i.e., the qualifying episode for their original study enrollment prior to enrolling in the RI period or a recurrence in RW which was treated with bailout rilonacept, whichever is the later). During this visit, the Investigator and subject will decide whether to continue treatment with open-label rilonacept, to continue in the study off-treatment for observation and rilonacept bailout upon subsequent recurrence, or discontinuation from the LTE. This review may be supplemented by cMRI and/or echocardiogram and/or additional diagnostic testing as determined by the Investigator. Subjects may also be unblinded at that time (if available) at the request of the Investigator per procedures outlined in the Unblinding Plan to assist in clinical decision-making.

[figure not shown]
Subjects completing the RW period are projected to be dosed with rilonacept for a minimum of approximately 36 weeks and a maximum of 2 years based on enrollment assumptions and pericarditis recurrence events accrual time. Subjects who enter the LTE will be dosed for up to 24-months longer.

Pericarditis Recurrence in the LTE Period (Observation arm)

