6.1.6. End of Randomized Withdrawal and LTE Baseline (EORW and LTE Baseline Visits)

All subjects, including those that have had pericarditis recurrence or have permanently discontinued study drug will have an EORW visit at the end of the RW period. Upon completion of the EORW visit procedures those subjects who have not discontinued treatment previously will provide informed consent to participate in the LTE period. The LTE Baseline visit will be completed on the same day as the EORW visit. During the LTE subjects will return to the site every 12 weeks for up to 24 months thereafter from the first dose of open-label rilonacept in the LTE. Refer to Section 13.1 for a comprehensive list of procedures in the Schedule of Activities for these visits.

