6.6.4. Non-fasting Lipid Panel

Subjects treated with riloncept may experience increases in their lipids, including total cholesterol, LDL, HDL, and triglycerides.

Non fasting measurements of total cholesterol, triglycerides, HDL, and direct LDL will be performed by central study laboratory as described in Section 13.1.

Investigators should monitor the lipid profiles in study subjects and consider ordering fasting lipid panel and/or lipid lowering therapies as needed based on cardiovascular risk factors and current guidelines.

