- v Study drug administration to occur only after subject provides informed consent for the open-label extension period.

Table 4: Study Schedule of Activities – Long Term Extension Treatment Period

Trial Period	LONG TERM EXTENSION (up to 24 months)			
	Long Term Extension Treatment (up to 24 Months) ^m			
Visit Name	LTE Week 12	LTE Week 24	LTE Every 12 Weeks	LTE 18-month Assessment ^{aa}
Visit Window ^b (days)	+/- 2	+/- 2	+/- 2	+/- 45
Visit Type	Clinic	Clinic	Clinic	Clinic
Concomitant medications	X	X	X	X
Pericarditis Concomitant medications	X	X	X	X
Full Physical Examination ^c		X		X
12-Lead ECG		X		X
Echo ^c		X		X
MRI		X ^z		X ^z
EQ-5D		X		
SF-36		X		
ISI		X		
PGIPS	X	X	X	
PGA-PA	X	X	X	
Hematology, Chemistry Labs (Central)	X	X	X	
Lipid Panel (Central) ^h		X		
CRP (Central)	X	X	X	X
PK (Central) ^s		X		X
ADA (Central) ^s		X	X ^{bb}	
Biomarkers (Central)		X		
Urine Pregnancy ^j (Local or Central)		X		X
Urinalysis		X		
IWRS Subject Status Update		X		X
IWRS Weight Input (pediatric only)	X		X	X
IWRS Drug Dispensing	X	X	X	X
In Clinic Study Drug Administration ^o	X	X	X	
Outpatient Study Drug Administration ^o	WEEKLY			
Study Drug Compliance Review	X	X	X	X
Assessment of Pericarditis Recurrence	X	X	X	X
Adverse Event Reporting ^l	X	X	X	X

- a The screening and enrollment visit can be combined.
- b Scheduling of visits within visit windows requires cautious planning to ensure there is no interruption to subject evaluation and study drug treatment.
- c Full physical examination includes at minimum evaluation of vital signs, head, eye, ear, nose, and throat as well as cardiovascular, dermatological, musculoskeletal, respiratory, GI, genitourinary, and neurological systems. The decision to perform examination of genitourinary system should be guided by clinical judgement.
- e ECHO is required to be obtained according to the central core lab parameters and then read locally and submitted to the central core lab for separate review and analysis.
- h Lipid panels are non-fasting and are to be drawn at a minimum of every 6 months during the randomization withdrawal and LTE periods, or more frequently as needed, with mandated evaluations as detailed in the schedule of events.
- j For women of child bearing potential - urine pregnancy testing can be repeated as needed throughout the course of the study and serum pregnancy can be drawn as needed; urine pregnancy is required to be performed at enrollment and 6 weeks after the last dose of study drug.

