- l Adverse event reporting begins following the subject providing informed consent.
- m All procedures are to be completed prior to study drug administration.
- o Study drug administration is once weekly with a minimum of 5 days required between doses.
- s PK and ADA samples will be collected prior to study drug administration. PK at enrollment/baseline will be taken from ADA. As required, ADA samples will be collected at EOS, ET, and Unscheduled visits.
- z The MRI to occur only if the previous MRI was done longer than 6 months ago.
- aa Visit to occur 18 months from most recent documented recurrence.
- bb Samples collected every 24 weeks.

Table 5: Study Schedule of Activities – Supplemental Visits

Visit Name	PERICARDITIS RECURRENCE ASSESSMENT	END of TREATMENT (EOT) ^x	SAFETY FOLLOW UP (SFU) ^y (6 weeks post last dose)
Visit Window ^b (days)	N/A	N/A	+/- 2
Visit Type	Clinic	Clinic	Clinic or TC/RN
Concomitant medications	X	X	X
Pericarditis Concomitant medications	X	X	X
Full Physical Examination ^c		X	
Abbreviated Physical Examination ^d	X		
Body weight and height	X		
12-Lead ECG	X	X	
Echo ^e	X ^e	X	
MRI (substudy only)		X ^z	
Pericardial pain (11-point NRS)	X	X	
EQ-5D	X	X	
SF-36	X	X	

Visit Name	PERICARDITIS RECURRENCE ASSESSMENT	END of TREATMENT (EOT) ^x	SAFETY FOLLOW UP (SFU) ^y (6 weeks post last dose)
Visit Window ^b (days)	N/A	N/A	+/- 2
Visit Type	Clinic	Clinic	Clinic or TC/RN
ISI	X	X	
PGIPS	X	X	
PGA-PA	X	X	
Hematology, Chemistry Labs (Central)		X	
Lipid Panel (Central) ^h		X	
CRP (Local)	X		
CRP(Central	X	X	
PK (Central) ^s	X	X	X
ADA (Central) ^s	X	X	X
Biomarkers (Central)	X	X	
Urine Pregnancy ^j (Local or Central)			X
Urinalysis		X	
IWRS Subject Status Update	X ^s	X	
IWRS Weight Input (pediatric only)	X		
IWRS Drug Dispensing	X		
Study Drug Compliance Review	X	X	
Assessment of Pericarditis Recurrence	X	X	X
Adverse Event Reporting ^l	X	X	X

- b Scheduling of visits within visit windows requires cautious planning to ensure there is no interruption to subject evaluation and study drug treatment.
- h Lipid panels are non-fasting and are to be drawn at a minimum of every 6months during the randomization withdrawal and LTE periods, or more frequently as needed, with mandated evaluations as detailed in the schedule of events.

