13.3. Summary of Changes

This summary of changes document has been prepared to summarize changes to clinical protocol study KPL-914-C002 Amendment 2 (Version 3.0) when compared with the previous amendment (Version 2.0) dated 12 April 2019. The primary reason for this protocol amendment is to increase the ability to assess impact of length of treatment. A summary of the major protocol changes is described below including a rationale for change. In addition, the presentation of content was revised according to the Sponsor’s template; no changes to the content of the study were altered as a result of this change unless otherwise specified below.

Section(s) Impacted	Protocol Change	Reason for Change
Global	Primary efficacy endpoint analysis triggered at 22 CEC events. Requirement for a full 24 weeks follow-up dropped for all subjects.	Study powered for time to event; increased enrolment ensures safety exposures are adequate.
Global	LTE extended to 24 months. Observation follow-up dropped.	Provide longer access to study drug for study participants.
Global	Other minor administrative and editorial changes were made throughout the protocol.	Provided for consistency and clarification purposes.

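### Table 4 schedules one lipid panel, at LTE Week 24, but footnote h on the same row requires one at least every 6 months in an extension of up to 24 months

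*Protocol*

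**What the plan says.** The current text is protocol version 3.0 (Amendment 2).

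- **Table 4, footnote h, attached to the Lipid Panel row:** "Lipid panels are non-fasting and are to be drawn at a minimum of every 6 months during the randomization withdrawal and LTE periods". The footnote then allows extra draws as needed and says that the mandatory ones are those shown in the schedule.
- **Table 4, the row itself:** one mark, at LTE Week 24. The columns for LTE Week 12, the recurring 12-weekly visits and the 18-month assessment are blank.
- **Section 6.1.6, LTE visits:** "During the LTE subjects will return to the site every 12 weeks for up to 24 months".
- **Section 6.6.4, on how lipids are measured:** "Non fasting measurements of total cholesterol, triglycerides, HDL, and direct LDL will be performed by central study laboratory as described in Section 13.1". It gives no frequency of its own.
- **Table 4, ADA row:** marked at LTE Week 24 and again under the recurring 12-weekly column, with note bb: "Samples collected every 24 weeks".
- **Other lipid marks:** Table 3 has one at the EORW visit, which is also the LTE baseline. Table 5 has one at the end-of-treatment (EOT) visit.

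**The concern.** The row and its footnote give different schedules. The footnote sets a 6-monthly minimum over the whole LTE. The grid, to which the footnote defers for the mandatory panels, stops after the first one. A site working from the grid draws nothing on schedule between LTE Week 24 and EOT. A site working from the footnote draws every 6 months. Each can cite the protocol.

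This matters because raised lipids are a stated effect of rilonacept (Sections 1.3.1 and 6.6.4), and Section 6.6.4 asks for action on them: "Investigators should monitor the lipid profiles in study subjects and consider ordering fasting lipid panel and/or lipid lowering therapies as needed". The prescribing information appended to version 2.0 (its section 6.7) reports a mean triglyceride rise of 57 mg/dL after 6 weeks of open-label treatment in CAPS patients. If sites read the table differently, both the monitoring of patients and the completeness of the long-term lipid data will vary by site.

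**Working it through.** The plan states no figure that bears on this point, so there is none to reproduce. The check is a reading of the table followed by a count of weeks.

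**Is the mark in the right column?** Biomarkers, urinalysis, EQ-5D, SF-36 and ISI are also marked only at LTE Week 24. Hematology/chemistry, CRP and ADA do carry marks under the recurring 12-weekly column. A column shift in the extracted text is therefore unlikely.

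**Inputs.** LTE of up to 24 months (Table 4 header and Section 3.1.4); visits every 12 weeks (Section 6.1.6); at most 6 months between panels (footnote h); one marked panel, at Week 24 (Table 4).

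**Conversion.** 365.25 / 12 / 7 = 4.348 weeks per month. So 24 months = 104.4 weeks and 6 months = 26.1 weeks. Below I round to 104 and 26, with 18 months = 78 and 12 months = 52.

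**Gap after the only marked panel** = LTE length − 24. **Missing 24-weekly draws** are those after Week 24 within the LTE.

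| LTE length | Gap from Week 24 to end of treatment | 24-weekly draws not marked |
|---|---|---|
| 12 months (52 weeks) | 52 − 24 = 28 weeks | 1 (Week 48) |
| 18 months (78 weeks) | 78 − 24 = 54 weeks | 2 (Weeks 48, 72) |
| 24 months (104 weeks) | 104 − 24 = 80 weeks | 3 (Weeks 48, 72, 96) |

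The longest gap is 80 / 26 = 3.1 times the permitted interval.

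**Where the breach starts.** The EOT panel closes the gap, so the 6-month limit is exceeded only when LTE treatment runs beyond 24 + 26 = 50 weeks.

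**What the visit grid allows.** Visits fall at Weeks 12, 24, 36, 48, 60, 72, 84 and 96. The longest spacing on that grid that stays within 26 weeks is 24 weeks, giving draws at Weeks 24, 48, 72 and 96. The grid marks one of these four. The count leaves out the LTE-baseline panel at EORW, which is marked.

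**How it arose.** In version 2.0, LTE treatment lasted 24 weeks (its Table 1–3), and a single Week 24 mark satisfied the same footnote. The Summary of Changes for Amendment 2 records "LTE extended to 24 months". Version 3.0 gives the ADA row a 24-weekly note in the recurring column; the lipid row kept its single mark.

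**The case against.** The strongest reply is that grid and footnote can be read together. Footnote h hangs on the row label, so anyone using the row is sent to it. It sets a standing minimum, and a blank cell forbids nothing. Table 3 follows the same pattern: its open-ended 8-weekly columns are blank for lipids under the same footnote, as they were in version 2.0. ADA needed note bb because no other footnote gave it a frequency.

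It can also be said that 80 weeks is a worst case. Section 3.1.4 lists several ways for treatment to end ("Treatment in the extension period may continue until the earliest of the following dates"), including commercial approval or reimbursement. The 18-month review is timed from the most recent recurrence, not from LTE entry. With the projected minimum of about 36 weeks of dosing by the end of the RW period, a subject with no RW recurrence reaches that review at about LTE Week 78 − 36 = 42 or earlier, within a ±45-day window. Stopping then would bring an EOT panel. In addition, Section 6.6.4 independently asks for lipid monitoring, the DMC reviews safety during the LTE, and Section 7.7.8 specifies no LTE lipid summary.

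Much of this stands. The footnote does bind, the worst case is a ceiling, and no efficacy result is touched. The mismatch remains, though. The footnote returns the reader to the grid for the mandatory panels, and the grid has none after Week 24. The blank columns in Table 3 show the same weakness elsewhere and do not cure this one. The early review does not help subjects who continue treatment, had a late RW recurrence or entered the LTE directly from the run-in. EOT is a single draw and cannot supply those due during treatment. It is not even certain for a subject who completes 24 months, because Section 6.1.7 ties it to premature discontinuation while footnote x to Table 5 ties it to permanent discontinuation.

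**Conclusion.** The concern holds. As written, Table 4 does not implement the lipid schedule that its own footnote requires, and no other section does so. If the grid is followed, the unscheduled interval is 28 weeks in a 12-month LTE, 54 in an 18-month LTE and 80 in a full 24-month LTE, against about 26 allowed.

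These figures assume that the site works from the grid alone, that an EOT panel is drawn when treatment stops, and that no extra lipids are ordered on clinical grounds. The defect is the disagreement between row and footnote; the protocol does contain a lipid requirement. Its effect is confined to safety monitoring and long-term lipid data in the uncontrolled extension.

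**What to change.** In the Lipid Panel row of Table 4, add a mark under the recurring 12-weekly column with note bb, as the ADA row already has. Together with the existing Week 24 mark this gives draws at LTE Weeks 24, 48, 72 and 96, each 24 weeks apart and within the 6-month limit, and the row then agrees with footnote h.

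The cost is one table entry and up to three panels per subject. Footnote h already requires those panels. They are non-fasting and fall at visits where central chemistry, hematology and CRP are already drawn.

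While the table is open, the blank 8-weekly columns of the lipid row in Table 3 deserve the same look: an RW stay beyond about Week 24 + 26 = 50 would raise the same question.

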13.2. Appendix: 11-point Numerical Rating Scale (NRS) for Assessment of Pericarditis Pain

Subjects will be asked to select the score that best describes their average level of pericarditis pain over the previous 24 hours using an 11-point NRS, where zero (0) indicates ‘no pain’ and ten (10) means indicates ‘pain as bad as it could be’.

0	1	2	3	4	5	6	7	8	9	10
---	---	---	---	---	---	---	---	---	---	----

On this scale of 0-10, zero (0) indicates ‘no pain’ and ten (10) indicates ‘pain as bad as it could be’, please rate your pericarditis pain on average in the last 24 hours

13.3. Summary of Changes

This summary of changes document has been prepared to summarize changes to clinical protocol study KPL-914-C002 Amendment 2 (Version 3.0) when compared with the previous amendment (Version 2.0) dated 12 April 2019. The primary reason for this protocol amendment is to increase the ability to assess impact of length of treatment. A summary of the major protocol changes is described below including a rationale for change. In addition, the presentation of content was revised according to the Sponsor’s template; no changes to the content of the study were altered as a result of this change unless otherwise specified below.

Section(s) Impacted	Protocol Change	Reason for Change
Global	Primary efficacy endpoint analysis triggered at 22 CEC events. Requirement for a full 24 weeks follow-up dropped for all subjects.	Study powered for time to event; increased enrolment ensures safety exposures are adequate.
Global	LTE extended to 24 months. Observation follow-up dropped.	Provide longer access to study drug for study participants.
Global	Other minor administrative and editorial changes were made throughout the protocol.	Provided for consistency and clarification purposes.
